#### Analysis of New Start program data

We will analyse of characteristics of clients testing through the New Start model descriptively. Factors associated with opting for self-testing will be investigated, with odds ratios and 95% confidence intervals computed using logistic regression. Rates of linkage to HIV care and VMMC for clients and partners of HIV positive clients will be investigated using appropriate models.

## **7 DISSEMINATION OF RESEARCH FINDINGS**

A report on the study will be produced and disseminated to the Zimbabwean Ministry of Health and Child Care. Results of the study will also be disseminated to the communities participating in the research, regionally and internationally through conference presentations and publications.

Quarters (2016-2017)	Q1		Q2		Q3		Q4		Q5			Q6						
Month (2016-2017)	J	F	М	А	М	J	J	А	S	0	Ν	D	J	F	М	А	М	J
Ethical approval of the study	х	х	х															
Finalise model for kit distribution based on pilot study results				х														
Recruitment and training of community based distributors				х														
Community based kit distribution					х	х	х	х	х	х	х	х	х	х	х	х		
Household surveys						х	х	х	х	х	х	х	х	х	х	х	х	
DCE on linkage to care						х												
Process evaluation including qualitative studies						х	х	х	х	х	х	х	х	х	x	х	х	
Data analysis																	х	x

## Appendix 1: Standard Operating Procedures for the New Start Model

#### Overview

Distribution will occur at six PSI outreach New Start Centres in Harare, Bulawayo, Chitungwiza, Masvingo, Mutare and Gweru. Three channels of HIVST distribution will be employed: 1) distribution at static sites through the offer of a choice between PDHTC or HIVST; 2) distribution to partners of individuals who test HIV positive at the static sites, and 3) distribution during testing and counselling outreach in urban areas in Bulawayo and Harare

Clients who opt for HIVST can either test onsite, or, if they are able to provide the relevant contact information, take the kit for off-site testing at a time that is convenient to them.

Clients who are confirmed HIV positive through PDHTC will be offered the possibility of taking an HIVST away for their partners to use.

#### Outcomes from the pilot distribution at New Start facilities:

- 1. Proportion of clients seeking HTS at static centres who opt for HIVST
- 2. Proportion of clients who opt for HIVST who choose to test-onsite
- 3. Among clients who choose to self-test on-site, the proportion who self-test positive and are confirmed positive through PDHTC
- 4. Among clients who choose to test off-site, proportion reporting testing within (i) two weeks, (ii) four weeks, (iii) three months
- 5. Among clients who choose to test off-site, proportion reporting linkage to appropriate prevention and care services, by three months, to (i) confirmatory testing, if self-test result was positive, and, (ii) voluntary medical male circumcision (VMMC), if male, uncircumcised and tested negative, iii) PrEP among HIV negative at risk individuals
- 6. Among PDHTC clients who test HIV positive, proportion who accept HIVST kit for partner
- 7. Among PDHTC clients who accepted self-test kit for partner, proportion who report giving kit to the partner
- 8. Among PDHTC clients who accepted self-test kit for partner, proportion reporting testing of partner within (i) one week, (ii) two weeks, (iii) one month
- 9. Among PDHTC clients who accepted self-test kit for partner, proportion aware of partner's self-test result
- Among clients who collect self-test kit for partner, proportion reporting linkage of partner, by three months, to (i) confirmatory testing, if partner obtained a positive self-test result; (ii) VMMC, if partner is male and obtained a negative self-test result

#### **Detailed procedures:**

#### Offer of HIVST at Static New Start Centres

The offer of self-testing at static facilities will be done according to the figure below.

## Methods for distributing self-test kits at static sites

#### Direct distribution to clients

At the six static sites, clients will be told about the option to self-test and invited to watch an instructional video about HIVST. They will be then be given a choice between PDHTC or HIVST. Those who opt for self-testing will have the choice of testing on site or taking the kits away for testing at their convenience.

#### Clients choosing to test on site

Clients who choose to self-test on-site will be given a self-test package and access to a cubicle or room where they can self-test in private. The self-test package will consist of the kit, validated testing instructions, and a result form where the client will write down the result of the HIV self-test. At the time of receiving the package participants will be shown an instructional video on a computer, tablet, smartphone or television screen. They will also provide information that New Start routinely collect from clients seeking HTS, including demographic information and history of HIV testing; these data are collected electronically. The results form and electronic form will only be identified by barcoded identity numbers. In a separate database, the client's name, home address, mobile telephone number and bar-coded identity number will be recorded. Where possible, mobile phone numbers will be verified by ringing.

Clients will be asked to place their used test kits, together with the results form, in a dropbox that will be at the facility. They will be told that they do not have to disclose their self-test results to New Start staff. However it will be emphasized that should they obtain a positive self-test result, confirmatory HIV testing is necessary and will be available on-site on the same day. Confirmatory testing will be offered according to usual procedures for provider-delivered testing. In addition they will be advised that if they are HIV negative there are HIV prevention interventions that they may wish to consider (VMMC or PrEP).

## Clients choosing to self-test off site

Clients choosing to test off-site will be given the self-test package and will be shown the instructional video, as per those testing on site. In addition, they will be given detailed instructions on how to seek post-test support services, including confirmatory testing if needed. In order to restrict the use of self-test kits to the intended purpose, clients eligible for taking kits away must be:

- Willing to provide a telephone number that *must* be verified through ringing at time of kit distribution
- Willing to receive telephone calls from New Start staff. These calls will be to check whether the participant has self-tested, and if required, whether he/she has linked to care. Participants will provide verbal consent to this effect.

Participants who cannot meet the above criteria will be asked to self-test on site or to take up provider-delivered testing.

At the time of collecting the self-test kit, participants will be asked to think about the date and time they are likely to self-test, and to write these down on an appointment card which they will keep (previous research has shown that this approach improves completion of health tasks or health-related appointments) [23, 24]. The 'appointment date' will also be recorded together with the participant's other electronic data.

Participants who take self-test kits away will be asked to drop off the used test kits with the results form at the nearest New Start Centre or nearest polyclinic (kits and results forms are only identified by bar codes with no client names). New Start Staff will regularly collect the used kits from the drop-off sites for late reads as described in section 4.2.3 of the protocol.

At two weeks after collection of the kit, a random selection of the clients who took kits away will be telephoned to ask if they self-tested, and the result of the self-test. 200 clients will be telephoned per month based on a sampling fraction that alters every month depending on number of clients who have opted to take self-test kits away. If the self-test was positive, they will be asked whether, when and where they sought confirmatory testing. Males whose self-test result was negative will be asked whether, when and where they went for VMMC. This information will be updated on the participant's electronic record. Women who have tested negative will be asked if have considered PrEP.

Participants who had not tested at two weeks, or had not linked to services as applicable, will be given another call at 4 weeks and at three months. To ensure that participants' confidentiality is maintained and that telephone interviews are conducted with the correct person, staff who do the telephone calls will verify the following information before proceeding:

- Name of participant
- Date of birth

• Correct response to a 'password' question that is completed at time of kit collection according to participant's preference, for example name of primary school that was attended, mother's maiden family name, etc

**NOTE:** there is a requirement by funders of this programme to determine rates of linkage which is independent of the research. PSI are routinely following clients to determine linkage as part of their programme activities

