## 4.3 Pilot HIVST kit distribution at New Start HIV testing Centres

Distribution will occur in six geographic areas where New Start HIV testing services are offered in the following cities: Harare, Bulawayo, Chitungwiza, Masvingo, Mutare and Gweru. Three channels of

HIVST distribution will be employed: 1) distribution at static sites through the offer of a choice between PDHTC or HIVST; 2) distribution to partners of individuals who test HIV positive at the static sites, and 3) distribution during testing and counselling outreach in urban areas in Bulawayo and Harare. In this model we aim to:

- 1. Determine the acceptability of HIVST among individuals who seek HTS within New Start static and mobile sites in urban areas
- 2. Determine HIV yield among clients who are given HIV self-test kits compared to those who opt to test using PDHTC
- 3. Measure uptake of self-test kits for partners among clients who have tested HIV positive at New Start Static sites
- 4. Determine rates of linkage to HIV care, voluntary medical male circumcision (VMMC), and PrEP (offered to women aged 18-24) among individuals who are given HIV-self-test kits
- 5. Determine the cost and cost-effectiveness of providing HIVST through New Start HIV testing services

Detailed procedures are given in Appendix 1, Standard Operating Procedures (SOP) for the New Start Model.

Late read of returned used self-test kits will be done as detailed in the SOP. In addition, a visual stability study of used test kits will be done at New Africa House New Start Centre. Participants who give verbal consent for their used test kits to be anonymously used in the study will place their used test kit in a separate drop box that is earmarked for this purpose. This drop box will be emptied every ten minutes for immediate late read of results (as opposed to the regular drop box which will be emptied on a weekly basis. The visual stability study procedures are detailed in Appendix 1a. In brief, all test kits collected for the visual stability study will be re-read at regular intervals, under ambient conditions in the PSI laboratory, for a period of 12 months.

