## Offer of kits for partners of HIV positive clients

Individuals who test positive during PDHTC will be offered a self-test kit for their regular partner/s. Participants will be encouraged to check with their partner if they may want a self-test kit, and to check if the partner is happy to have their contact details passed on to study/program staff. In addition to the kit and instructional materials (a whatsapp version of the video will be shared with the participant if he/she has whatsapp) that are given as per clients taking the kits themselves, an information sheet that is addressed to partners will be enclosed. Only individuals who meet the following criteria will be eligible for taking kits to their partner:

- Willing to offer an HIV self-test kit to partner
- Willing to provide a telephone number that *must* be verified through ringing at time of kit distribution
- Willing to receive telephone calls from New Start staff. These calls will be to check whether the participant has given the kit to his/her partner, whether the partner tested, and whether, when or where the partner linked to confirmatory testing (if result of self-test was positive) male circumcision (if male and self-test result was negative), or PrEP, if at risk of HIV acquisition.
- Willing to give the partner's contact details for contact by the study team.

Clients will be told that a positive self-test result necessitates a confirmatory test, which must be provider-delivered. They will be told about possible places where confirmatory testing can be accessed if needed.

At two weeks after collection of kit, the client will be telephoned to ask if he/she gave the kit to the partner, whether the partner accepted it, whether the partner self-tested, and the result of the self-test if known. If the self-test was positive, they will be asked whether, when and where the partner sought confirmatory testing. Participants whose male partner's self-test result was negative will be asked whether, when and where the partners went for VMMC. Participants reporting that their partner obtained a negative self-test result will be asked if the partner linked to PrEP. This information will be updated on the participant's electronic record.

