Participants who, at two weeks, had not yet given the kit to their partner (and report intention to do so), or those whose partner accepted the kit but had not tested at two weeks, or had not linked to services as applicable, will be given another call at 4 weeks and at three months. To ensure that participants' confidentiality is maintained and that telephone interviews are conducted with the correct person, staff who do the telephone calls will verify the following information before proceeding:

- Name of participant
- Date of birth
- Correct response to a 'password' question that is completed at time of kit collection according to participant's preference, for example name of primary school that was attended, mother's maiden family name, etc.

If the participant reports that the kit was given to her partner, at four weeks the partner will be telephoned to determine whether he/she self-tested, and the result of the self-test. If the self-test was positive, they will be asked whether, when and where they sought confirmatory testing. If the self-test result was negative and the partner is male, he will be asked whether, when and where he went for VMMC. Partners reporting a negative self-test result will be asked if, when where they linked to PrEP.

To ensure that the partner's confidentiality is maintained and that telephone interviews are conducted with the correct person, at time of collecting the kit from program staff, participants will be asked to share their 'password' information above with their partners. This information will be verified with the partner before the telephone interview can proceed.

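### New Start pilot: the follow-up calls as described do not measure PrEP linkage for off-site self-testers (outcome 5(iii)) or partner testing within one week (outcome 8(i))

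*Protocol*

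**What the plan says.** **PrEP among clients who self-test off site.** Protocol section 4.3, aim 4, is to determine linkage to several services among people given kits, including "PrEP (offered to women aged 18-24"). The outcome list in Appendix 1 makes this item 5 for off-site testers: "proportion reporting linkage to appropriate prevention and care services, by three months", with third component "iii) PrEP among HIV negative at risk individuals".

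The section of Appendix 1 on clients choosing to self-test off site describes a telephone call at two weeks to a random selection of these clients, 200 per month. Clients with a positive self-test are asked if, when and where they had confirmatory testing. Men with a negative result are asked the same about VMMC. On PrEP the section says: "Women who have tested negative will be asked if have considered PrEP". Clients who had not tested, or had not linked to the services that apply to them, are called again at four weeks and three months.

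**Partners of clients who test positive.** Outcome 8 is the "proportion reporting testing of partner within (i) one week, (ii) two weeks, (iii) one month". The index client is called at two weeks and asked, among other things, "whether the partner self-tested, and the result of the self-test if known". Repeat calls at four weeks and three months go to those with something outstanding. The partner is called at four weeks and asked about self-testing and its result. On PrEP, this channel says: "Partners reporting a negative self-test result will be asked if, when where they linked to PrEP".

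**The concern.** Appendix 1 is the operating procedure for the pilot, and it says what callers are to ask. If they ask what it describes, two listed outcomes have no matching data.

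- For PrEP, the outcome is an action (linkage) with a time limit (three months). The item records a state of mind, from women only.
- For partners, a one-week window is to be estimated from calls that start at two weeks and record no test date.

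PrEP linkage is part of a stated pilot aim. An answer not collected during the calls is hard to recover later, so the remedy has to come before or during follow-up and cannot be left to the analysis. This is also why the point is more than detail that an analysis plan could supply: no analysis turns 'considered' into 'linked', or a yes at two weeks into a date.

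**Working it through.** No sample size, power or other figure is involved, so there is nothing to recompute. The check sets each outcome beside the call content and call times in Appendix 1.

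**1. Outcome 5 (off-site clients), by component**

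| Component | What the outcome needs | What the client call asks | Match |
|---|---|---|---|
| (i) Confirmatory testing | Linkage by three months, if self-test positive | If, when and where | Yes |
| (ii) VMMC | Linkage by three months, if male, uncircumcised and negative | If, when and where, of negative men | Yes |
| (iii) PrEP | Linkage by three months, if negative and at risk | If considered, of negative women | No |

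The PrEP item differs from its outcome in three ways: the event (considering, not linking), the people asked (women only) and timing (no date or place). The first two components show that the same call can ask the right question. The partner channel shows that the SOP already has suitable PrEP wording: "Partners reporting a negative self-test result will be asked if, when where they linked to PrEP".

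The partner channel has the reverse mismatch. It collects PrEP linkage, but the partner linkage outcome at the end of the list names only confirmatory testing and VMMC.

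**2. Repeat calls.** The four-week and three-month calls depend on whether the client has linked as applicable. If the two-week answer on PrEP is only that it was or was not considered, the caller cannot tell whether a negative woman still needs those calls. The three-month time point of outcome 5(iii) is therefore affected as well as the two-week answer.

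**3. Who is counted for PrEP**

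| Place | Group named |
|---|---|
| Section 4.3, aim 4 | Women aged 18-24 (as those offered PrEP) |
| Appendix 1, outcome 5(iii) | HIV-negative individuals at risk |
| Appendix 1, off-site client call | Women who tested negative |

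Within the negative clients, the first group is nested in the third and could be picked out by age, since demographic data are collected. The second group is not nested in either: it is not limited by sex or age, and it is limited by risk, for which no call item is described.

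**4. Outcome 8 (partner testing), by window**

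| Window | Nearest call | Obtainable from a yes/no answer? |
|---|---|---|
| (i) One week | None; first call at two weeks | No |
| (ii) Two weeks | Index client, two weeks | Approximately, if the call is on time |
| (iii) One month | Index client or partner, four weeks | Approximately, if the call is on time |

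A partner who tested on day 3 and one who tested on day 12 both give a yes at two weeks. Only the first belongs in window (i), and nothing asked separates them. In this channel 'when' is attached to confirmatory testing, VMMC and PrEP, never to the self-test. Outcome 4, for off-site clients, has no such problem: its windows (two weeks, four weeks, three months) are the call times.

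**5. Other possible sources of a test date.** The appointment card described for off-site clients holds an intended date. The results form is described as recording the result. Neither is described as giving the partner's actual test date.

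**The case against.** The strongest reply is that one sentence of procedure is being read as the whole instrument. The same section says the calls check, where required, whether the client has linked to care. The repeat-call rule presupposes that callers know whether the client has linked to applicable services. A note adds that the programme follows clients routinely to determine linkage, independently of the research. The telephone form itself is not shown and might hold a PrEP linkage item or a test date.

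This softens the gap but does not close it. None of these general statements mentions PrEP, and the one sentence that does asks something else. Where the SOP intends linkage to be asked, it says so, as for confirmatory testing, VMMC and the partner's PrEP. Nor does any text mention the partner's test date.

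A second reply is that the women-only item follows from section 4.3, which has PrEP offered to women aged 18-24. That explains part of it, and the call does cover that group. It does not reconcile the item with outcome 5(iii), and PrEP is mentioned without a sex limit in the on-site testing section and in the partner calls.

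A third reply is that these are descriptive outcomes of a pilot that is a secondary objective. That stands, and it limits the weight of the point.

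Two stronger readings are tempting. A reader might infer that reported PrEP linkage will be too high by some multiple. The documents give no rate for considering or starting PrEP, and nowhere say that 'considered' would be reported as 'linked', so no such figure can be derived. A reader might also infer that outcome 8 fails as a whole. It does not: only its one-week window is lost.

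**Conclusion.** The point holds within these limits. As described, the off-site client call does not measure outcome 5(iii), and the aim, the outcome and the call name different groups for PrEP. Outcome 8(i) cannot be obtained from the described calls, while 8(ii) and 8(iii) can be approximated if calls are on time.

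In size, this is one of three components of outcome 5 and one of three windows of outcome 8. Both are descriptive outcomes of the New Start pilot. The randomised comparison, its primary outcome and its power are untouched.

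The conclusion assumes that callers ask what Appendix 1 describes. If the form in use already records PrEP linkage for the outcome's group and the partner's test date, only the text needs correcting. The change should be made, because the data cannot be supplied at analysis, but it does not threaten the trial.

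**What to change.** 1. In the off-site client call, replace the PrEP item with whether, when and where the client linked to PrEP, as is already done for VMMC and in the partner's own call. Carry it into the four-week and three-month calls for clients not yet linked.
2. Reconcile section 4.3, outcome 5(iii) and the client call into one stated denominator, and ask the item of that group. Which group it should be is for the investigators. If the at-risk wording is kept, say how risk is established, since no described item does so.
3. Ask the date of the partner's self-test, or reset the outcome 8 windows to the call times, as outcome 4 already does.

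The cost is a few reworded call items and one aligned definition. Some extra repeat calls are possible, because clients who would otherwise need no further contact may now count as not yet linked to PrEP. Keeping the at-risk denominator may also require a risk item.
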